Stimuli Acquisition: Video cameras will be focused on the face of each partner to capture the content of the partner's speech as well as the partner's facial expressions during the discussion of a disagreement using two Canon VIXIA HF R400 video cameras. To ensure that there are not experimenter-introduced differences in the evocative stimuli used between groups in the subsequent experimental sessions, and to ensure we choose sufficiently arousing partner displays, stimuli selected will be according to the hierarchy of the Specific Affect (SPAFF) coding system (e.g., contempt, belligerence, criticism, defensiveness, stonewalling, respectively). It is important to note that conflict intensity differences likely naturally exist between DV couples and DNV couples (see Significance). Our method will ensure, however, that there are no experimenter introduced differences in the stimuli selected. Inter-rater reliabilities will be calculated on 50% of the videos and coders retrained to criterion if necessary. DV couples display at least 192 evocative behaviors per 15-minute disagreement discussion,⁶⁷ and partners are roughly equivalent in such displays¹⁸ ensuring ample evocative stimuli for subsequent sessions. Displays of these evocative behaviors also distinguish DNV from satisfied couples.⁴⁰ Partners will be excluded from the remainder of the study should the couple fail to provide sufficient stimuli. If the couple is symmetrical in violent behavior, one partner will be randomly selected to participate in the remaining sessions. If the couple is asymmetrical, the most violent partner will be selected for participation. DV partners will be matched and yoked to a DNV partner of comparable distress.

Emotion-Regulation Sessions: The selected partners (DV, DNV) will return to the laboratory on two separate occasions for the completion of the emotion-regulation sessions of the study. Once participants are prepped for biopotential recording, they will be administered either an alcohol beverage or placebo beverage (counter-balanced alcohol and placebo conditions; see below for procedures).

Alcohol Condition Protocol - Participants will receive a mixed drink (juice and 100-proof vodka) intended to raise their blood alcohol concentration (BAC) to a target dose of 0.08g% using a standard formula for calibrating the alcohol doses to achieve the target BACs.⁶⁸

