EEG, Psychophysiology and Pupillary Response Acquisition - EEG and psychophysiology data will be collected using the BrainVision actiCHamp 64-channel, DC amplifier, 24-bit resolution, biopotential system. EEG data will be recorded with filters set at 1 and 30Hz, digitized at a sampling rate of 512Hz and stored on a computer using the PyCorder software. EEG data will be recorded to collect a 5-minute baseline measurement prior to administration of alcohol or placebo beverage. After beverage administration data will be collected for the duration of the emotion-regulation task (see below). To reduce confounding results due to artifacts, EEG signals will be examined for contamination by muscle activity and eye movement. Fast Fourier Transformation (FFT) analysis will be applied to 6-10 second epoch samples (corresponding to the delivery of stimuli) allowing for 1-s pre- and post-stimuli artifact subtraction with the spectral graph ranging from 0 to 30Hz at 0.5Hz-resolution. FFTs will be performed using EEGLab software to calculate 1) Absolute power (AP; power density of each frequency band expressed in microvolts squared; mV^2/Hz); 2) Relative power (RP; proportional contribution of each band to the total power across 1 – 30Hz). AP and RP will be transformed into Fisher's z-scores for statistical analyses. Skin conductance (SC) will be collected using the BrainVision GSR module with leads placed on the left index finger and left middle finger. SC will be recorded to collect a 5-minute baseline (as with EEG) measurement and for the duration of the emotion-regulation task and time-locked to evocative stimuli. SC data will be subjected to detrending and transformed to Fisher's z-scores for statistical analysis. Respiration and HRV will be measured using an integrated BrainVision respiration belt, and an EKG in Lead II position. As with EEG, baseline measures will be collected, and time locked to evocative events. EKG data will be quantified as respiratory sinus arrhythmia (RSA) which is a unique measure of parasympathetic activity and self-regulatory ability. Respiration and HRV data will also be transformed to Fisher's z-scores for statistical analysis. Pupillary response data will be collected using the EyeLink 1000 system high speed camera by SR Research (see sample data). Corneal reflection will be recorded at 250 Hz. The left and right pupil diameter measures will be averaged offline and baseline measures (1 sec prior to trial onset) will be subtracted. The difference between the maximum diameter during the trial and the baseline diameter will be calculated and transformed to Fisher's z-scores for statistical analysis. E-prime will control the flow of the emotion regulation task and generate timestamps to denote conditions for which all biopotential data can be analyzed.

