
Emotion Regulation Task - The proposed approach for studying emotion regulation has been used in several previous studies,⁶⁹ but we will utilize participant-tailored stimuli (video clips of partner's evocative behavior). During viewing, participants will be instructed to 1) experience the emotion they associate with the video (WATCH), or 2) to suppress the feeling of emotion (DON'T REACT). In the WATCH condition, participants will be instructed to let their

emotional experience occur naturally, and to pay attention to how they feel during the clip. In the DON'T REACT condition, participants will be instructed to attempt to suppress any feelings of emotion so as to prevent an observer watching physiological recordings from knowing that an emotional response has occurred. In both conditions, participants will be asked to indicate their corresponding emotional state using a slider (clicking and dragging with a mouse) on a continuous rating scale anchored by "very negative" (1) and "very positive" (100). A total of 50 unique video clips between 4 and 8 seconds in length will be used in the task; 25 evocative and 25 neutral. Each stimulus will be presented twice: once in the WATCH condition and once in the DON'T REACT condition. On each trial, participants will view a blank screen (1 second), fixation cross (1.5 sec), blank screen (.5 sec), the instruction (WATCH or DON'T REACT; 1.5 sec), the video clip (4-8 sec), and a blank screen (up to 2.5 seconds). The total amount of time required for the task will be approximately 25 minutes. Ratings obtained during the emotion regulation task will be averaged across stimulus type and regulation condition for the placebo and alcohol sessions for statistical analysis.

Participant Remuneration: Each participant will be paid \$20 per hour for their participation in the study. Each partner will have the opportunity to earn \$40 for his/her participation in the *Stimuli Acquisition Session* (\$80 total). The partner invited back for the *Emotion-Regulation Sessions* will have the opportunity to earn \$100 for his/her participation in the *Alcohol beverage Emotion-Regulation Session* and \$20 in the *Placebo beverage Emotion-Regulation Sessions* for a total of \$200 per couple. Participants will receive remuneration in the form of Visa or similar gift cards.

12) List of Appendices

Scale Purpose	Scale Name	Use/Source	α	Population

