Plain Vanilla Task - The Plain Vanilla Task is a physiologically non-demanding task used to collect resting heart-rate variability data. In this task, the participant simply watches a computer screen for five minutes while it changes colors and reports how many times the screen turned blue. While the participant is watching the screen psychophysiological measurements of heart rate variability are collected. This task will only be completed during one individual session before any alcohol is consumed.

Emotion-Regulation Task – The approach for studying emotion regulation described below has been used in several previous studies of emotion regulation (e.g. Dan-Glauser & Gross, 2011). While this approach has used pictures from standardized stimulus sets, the methods from these studies will guide the current design.

Participants will view a video comprised of their partner's contemptuous, belligerent, critical, defensive, stonewalling and neutral behavior from the previous couple session. During this time physiological measurements will be collected including galvanic skin response (GSR), heart rate, respiration, and heart rate variability (inter-beat interval). Baseline measures will be taken where the participant sits quietly for five minutes.

While viewing the video clips, participants will be given instructions to 1) experience the emotion they associated with the video (WATCH), or 2) to suppress the feeling of emotion (DON'T REACT). In the WATCH condition, participants will be shown video clips and are instructed to let emotional experience to occur naturally, and to pay attention to how they feel during the clip. In addition, participants are instructed to record their feelings using a continuous visual analogue scale. In the DON'T REACT condition, participants are instructed to attempt to suppress any feelings of emotion so as to prevent an observer watching physiological recordings from knowing that an emotional response has occurred.

A total of 50 unique video clips will be used in the task, 25 negative and 25 neutral. These video clips will be between 4 and 8 seconds in length and will be determined by the PI using the standardized *Specific Affect Coding System*. Each stimulus will be presented twice: once in the WATCH condition and once in the DON'T REACT condition.

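### No clip brightness measurement or adjustment is planned for the pupil outcome, so the evocative-versus-neutral pupil effect is confounded with light; H1b carries avoidable noise, and bias only if the brightness difference differs between DV and DNV couples

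*Combined protocol and SAP*

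**What the plan says.** Section 11, under EEG, Psychophysiology and Pupillary Response Acquisition, averages the two pupils and then states that "baseline measures (1 sec prior to trial onset) will be subtracted". The score follows: "The difference between the maximum diameter during the trial and the baseline diameter will be calculated". Section 23 shows how the measure is read: a larger diameter is taken as more arousal.

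The clips come from one recorded disagreement per couple, filmed on the partners' faces "using two Canon VIXIA HF R400 video cameras". Under Stimuli Acquisition, "stimuli selected will be according to the hierarchy of the Specific Affect (SPAFF) coding system". Section 12 (Experimental Tasks) adds that the clips "will be determined by the PI using the standardized" SPAFF system. Neither statement names a physical property of the image.

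Under Emotion Regulation Task: "A total of 50 unique video clips between 4 and 8 seconds in length will be used in the task; 25 evocative and 25 neutral". Every clip is shown once under WATCH and once under DON'T REACT, after a run of other screens: "On each trial, participants will view a blank screen (1 second), fixation cross (1.5 sec), blank screen (.5 sec"), followed by the instruction.

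The Data Analysis Plan in Section 14 tests H1b as the partner type by stimulus type interaction, averaged over beverage. For H1c it relies on evocative stimuli being matched in arousal level between the two sessions. No section mentions brightness, luminance, screen or room lighting, or a covariate for any of these.

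**The concern.** The pupil responds to light as well as to arousal: it constricts when the image is brighter. The evocative and neutral clips are different footage, and each participant sees a different set. Each person's evocative-minus-neutral pupil score therefore contains a fixed term, the brightness difference between two sets of 25 clips. Showing the same clips again does not average it out. Subtracting a baseline recorded before the clip does not remove it either.

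If evocative clips tend to be darker, light alone would look like arousal. If they tend to be brighter, light would hide arousal. For H1b the consequences are lost precision and, if the brightness difference is not the same in DV and DNV couples, a spurious or masked group effect on the pupil outcome. EEG is checked for muscle and eye-movement artefact; the pupil measure has no equivalent check for light.

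**Working it through.** **No plan figure to reproduce.** The documents give no alpha, power, effect size or SD for any pupil contrast, and no derivation of 112 per group. Taken from the documents: 112 DV and 112 DNV partners; 25 evocative and 25 neutral clips; the trial sequence. Assumed here: two-sided alpha 0.05, all mm values, all light offsets, and two independent groups of participants.

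**1. Where the clip sits in the trial.** Trial length is 1 + 1.5 + 0.5 + 1.5 + (4 to 8) + up to 2.5 s, so 11 to 15 s with the longest final blank. Over 100 trials (50 clips × 2) this is 18.3 to 25.0 minutes, in line with the stated approximate 25. The clip fills 4/11 = 36% to 8/15 = 53% of the trial, so a maximum over the trial can fall on another screen.

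**2. What cancels in H1b.** Let L be the evocative-minus-neutral light effect in a group. H1b compares (evocative − neutral) in DV with the same difference in DNV, so its light bias is L_DV − L_DNV. This is zero when L is equal in the two groups.

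**3. False positives with no true arousal effect**, with offsets in SDs of the within-person evocative-minus-neutral score.
- Plain stimulus effect, all 224 participants: SE = 1/√224 = 0.067. A common offset of 0.1 SD gives a false positive in 32% of studies; 0.2 SD gives 85%.
- H1b with equal offsets: the rate stays at 5% (4.9% in 20,000 simulated studies with an offset of 0.3 SD in both groups).
- H1b with offsets differing by g: SE = √(2/112) = 0.134, and rate = Φ(g/SE − 1.96) + Φ(−g/SE − 1.96). For g = 0.05, 0.1, 0.2 and 0.3 SD this gives 6.6%, 11.6%, 32% and 61%.

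**4. Noise in H1b.** Let s be the brightness-driven SD between clips in the pupil score, and b the between-person SD of the contrast without it. With the same clips at every showing, the extra person-level SD is s × √(2/25), and the variance ratio is 1 + (extra/b)². The true effect is set to give 80% power when s = 0, that is (1.96 + 0.84) × 0.134 = 0.374 SD.

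| s (mm) | extra SD (mm) | variance ratio, b = 0.10 | power | variance ratio, b = 0.15 | power |
|---|---|---|---|---|---|
| 0.05 | 0.014 | 1.02 | 79% | 1.01 | 80% |
| 0.1 | 0.028 | 1.08 | 77% | 1.04 | 79% |
| 0.2 | 0.057 | 1.32 | 68% | 1.14 | 75% |
| 0.3 | 0.085 | 1.72 | 57% | 1.32 | 68% |

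**The case against.** A reader might infer that H1b itself partly measures light. The documents do not support that as a statement about bias. H1b is an interaction, and a light difference shared by the two groups drops out. Section 11 expects DV and DNV couples to differ in conflict intensity. It says nothing about brightness, and any link through movement or head position is conjecture. The contrast that is plainly confounded, evocative versus neutral, is not itself a stated Aim 1 hypothesis.

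The size is also open. All clips of a participant's partner show the same face in the same session, filmed with one camera model, which limits the spread in brightness. At 0.05 mm between clips almost no power is lost; the 57% needs the least favourable value of both inputs. In addition, the score is a maximum over the trial and light constricts the pupil, so a bright clip need not lower a maximum reached on another screen. The mm calculation assumes that brightness passes fully into the score.

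The reach is narrow. EEG, skin conductance, respiration and RSA do not share this problem. WATCH versus DON'T REACT compares each clip with itself. H1c is largely protected if the same clips are used in both sessions, as the analysis plan implies.

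All of this stands, and it limits the point. It does not answer the core: the light term is in the pupil score, the baseline cannot remove it, and nothing planned would show whether it is small or differs by group.

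**Conclusion.** The point holds for one outcome and in a limited form. As planned, the plain evocative-versus-neutral pupil effect cannot be separated from clip brightness. Pupil H1b carries avoidable noise. It is biased only if the evocative-minus-neutral brightness difference differs between DV and DNV couples, which the documents neither show nor exclude.

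The loss of power ranges from negligible (about 80% retained) to substantial (57%) over the assumed SDs. If the groups' light offsets differed by 0.1 or 0.2 SD, the H1b false-positive rate would be 11.6% or 32% instead of 5%. These are illustrations under assumed inputs, not estimates for this study. H1c is largely protected on condition that clips are reused across sessions and that alcohol does not itself change the light response. The case for acting is that the term can be measured from video the study already keeps.

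**What to change.** 1. Compute the mean luminance of each clip from the stored video, and tabulate it by stimulus type and partner type. The table shows directly whether the condition for bias in H1b is met.
2. Score the pupil maximum within a prespecified clip window, not over the whole trial.
3. For the pupil outcome, test H1b with luminance as a covariate: either a trial-level model using the change from the preceding screen, or each person's evocative-minus-neutral difference in mean luminance. Show the unadjusted result alongside.
4. Keep the SPAFF hierarchy as the clip selection rule. Choosing clips to match luminance could disturb it, and the count of at least 192 evocative behaviours per discussion is given for DV couples only, so matching might succeed unevenly between groups.
5. State in the plan whether the same clips are used in both sessions. If they are, H1c does not need the covariate.

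The cost is one script and one extra model term (slightly more work if the model is at trial level), with no added participant time or staff. The adjustment can be applied to data already collected. The downside is that the covariate may absorb a little true response if movement in evocative displays changes luminance, which is why both results should be reported.

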Couples who meet eligibility criteria for study inclusion will be invited to come to the UNM CTSC where they will receive detailed information about the study components and procedures, including the 15-minute discussion of a disagreement, and will have the opportunity to ask any questions that they have about participating. Participants will receive a full written informed consent document. The informed consent form will reiterate the experimental procedures, monetary compensation, risks and benefits, confidentiality of all data obtained, and the voluntary nature of all components of the study. The consent form will also ask the participants if their video segments may be used for training of research staff. In order for this to occur, both partners must provide permission and are free to retract this permission at any time without it affecting the rest of their study participation. The consent form will be approved Human Research Review Committee at the University of New Mexico prior to use. The PI, co-investigator or other research associate will be responsible for obtaining informed consent. The language used in the consent form will be easy to understand, participants will be reminded that they are free to not participate, or discontinue participation at any time during the study. If, however, it is during the alcohol administration condition the participant must wait until their BAC is .03 or lower and participants must be not be displaying any angry affect greater than "feeling somewhat negative" prior to leaving the research site. Participants will also be informed that they are free to withdraw any information provided during the study, including erasing portions of the video recording. Should a participant make this request, it would result in the exclusion of the couple from further procedures and participation in the study as their video-taped communication discussion will be used as stimuli in subsequent study phases.

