2. Monitoring of the occurrence of adverse events will occur after each study session and one week after the last study session. Monitoring of adverse events will be conducted via a telephone call to each partner the day following a study session and to each partner, again, one week after the completion of all study sessions. The purpose of this monitoring is to ensure that study sessions were not responsible for violent arguments between the partners. Objectivity in assessing adverse events will be ensure by proper training by the PIs and an immediate notification of both PIs if an adverse event has occurred. Additionally, a PI will follow-up with the partners to confirm the details of such an event.

Because this study also involves an alcohol administration procedure, we also have protections surrounding the consumption of alcohol and will be monitoring this for adverse events, as well. First, participants must be weekly drinkers and must have reported at least two binge drinking episodes in the previous month (>4 drinks for males, >3 drinks for females); therefore, the study will not use alcohol-naïve participants, but individuals who routinely reach the level of blood alcohol concentrations that will be obtained during the study procedures. Secondly, the participants must remain in the laboratory until their blood alcohol concentration falls to between .02% - .04%. Note that this level is within the recommended range (.02% - .04%) for safe release of participants based on the NIH National Institute on Alcohol Abuse and Alcoholism (NIAAA) guidelines (<http://www.niaaa.nih.gov/Resources/ResearchResources/job22.htm>). Also consistent with NIAAA guidelines, release will require two consecutive readings of a BAC of .03% or below. During detoxification participants will be seated in a private room, given refreshments, and the choice of a variety of TV or movie comedies to view while their BAC is descending. Should a participant insist on leaving the lab before their BAC reaches .03%, the researchers will again calmly discuss the reasons for requiring the participant remain in the laboratory (e.g., physical safety of participant, etc.). If this is futile and the participant continues to insist on

leaving, the participant will be allowed to do so. If the participant is attempting to leave via driving his/her own vehicle, the police will be called and notified. This procedure will be disclosed to participants during the informed consent.

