2. To protect against the risk of adverse outcomes for participants as a result of consuming alcohol, participants may discontinue their participation at any time, however, they will not be allowed to leave until after their BAC is below .03, consistent with NIH/NIAAA guidelines. In addition, because we are recruiting couples in which both partners consume alcohol, alcohol will not be administered to alcohol naïve participants as this would entail an unknown level of risk. Participants will also be provided with a detailed list of substance abuse providers and research staff will assist in arranging an appointment with the participant's top choice of treatment facility, if desired by the participant.
3. and 4. To protect against the aforementioned risk of discomfort resulting from the discussion of disagreement and the risk of partner violence as a result of the experimental procedure, we will follow procedures described by Gottman et al., 1995, except we will extend the procedures to the males in our pilot study. Both partners will separately complete an adjective checklist at the conclusion of each laboratory visit to assess the dangerousness of the situation. If any partner indicates he or she is feeling any negative emotion other than "feeling somewhat negative" the partner will be interviewed separately and the PI, a clinical psychologist with over eight years of working with violent couples, will use interviewing techniques to soothe the partner. UNM Campus Police will be informed of the study and will be on call within two minutes of the laboratory in the event they are needed. All participants (male and female) will also be given referrals to shelters, resources for obtaining legal representation and instructions on filing for orders of protection. Lastly, we will call each participant the night after each study procedure and one week after the last study visit to ensure that our study procedures did not lead to violent arguments. A violent argument is any argument resulting from participation in the study that leads to the use of physical aggression between partners, to include throwing or hitting the partner with an object.

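### Clip selection has no described masking to DV/DNV status and no rule within a behaviour category, so the assurance against staff-made group differences is not secured

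*Combined protocol and SAP*

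**What the plan says.** Section 12, under Emotion-Regulation Task, gives the choice of clips to the PI: "These video clips will be between 4 and 8 seconds in length and will be determined by the PI using the standardized" SPAFF system. Each task uses 25 evocative and 25 neutral clips.

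Section 11, under Stimuli Acquisition, describes two safeguards. The first is a ranking of behaviours: "stimuli selected will be according to the hierarchy of the Specific Affect (SPAFF) coding system", with contempt at the top and stonewalling at the bottom. The second is a check on coding: "Inter-rater reliabilities will be calculated on 50% of the videos and coders retrained to criterion if necessary". The same paragraph accepts that conflict intensity probably differs naturally between DV and DNV couples, and then states: "Our method will ensure, however, that there are no experimenter introduced differences in the stimuli selected".

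The PI may have contact with couples in three ways:
- Consent (Sections 11 and 28): "The PI, co-investigator or other research associate will be responsible for obtaining informed consent".
- End of a visit, if a partner reports more than mild negative feeling (Section 17): "the PI, a clinical psychologist with over eight years of working with violent couples, will use interviewing techniques to soothe the partner".
- After an adverse event (Section 15): "a PI will follow-up with the partners to confirm the details of such an event".

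The only blinding mentioned anywhere is that of participants to beverage, in the pregnancy-test paragraph of Section 11. The numeric couple codes in Section 17 serve confidentiality and ensure that each participant sees the right footage.

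**The concern.** The clips are the experimental exposure, and each participant sees a different set. If the person choosing them knows, or can guess, which couples are violent, slightly stronger moments could be picked for DV couples without any intention to do so. DV participants would then respond more to evocative clips because the clips are stronger, not because the participants are more reactive. That is the pattern Hypothesis 1b predicts, so the bias would look like a confirmed hypothesis. The plan treats this possibility as excluded by its method, so the method has to be able to exclude it.

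**Working it through.** **1. What each safeguard covers.**

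| Decision in making a clip | SPAFF hierarchy | Reliability check on 50% of videos |
|---|---|---|
| Which behaviour code a moment receives | no | yes |
| Which category to use first | yes | no |
| Which moment within a category | no | no |
| Where the 4 to 8 second cut falls | no | no |
| Which neutral moments to use | no | no |

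The last three rows are left to the selector. Agreement between coders does not reach them. Even for the first row, coders who share knowledge of the group can agree and still be biased.

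**2. Room for choice.** Section 11 cites at least 192 evocative behaviours per 15-minute DV discussion and says partners contribute about equally. Only one partner's footage is used for a given viewer:

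192 / 2 = 96 behaviours, and 25 / 96 = 26%.

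About one in four available moments is used, before the hierarchy narrows the pool. No count is given for DNV couples.

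**3. Which hypotheses are exposed** (tests as set out in Section 14, Data Analysis Plan). Let δ be the extra evocative-minus-neutral response in DV participants that comes from clip choice alone.
- 1b (partner type × stimulus, averaged over beverage): expected contrast = true difference + δ. Fully exposed.
- 2c (partner type × stimulus × regulation, placebo only): exposed to the extent that stronger clips change the gap between WATCH and DON'T REACT. No beverage comparison removes it.
- 1c and 2d (the same contrasts, alcohol against placebo within person): δ cancels if it is equal in both sessions. It remains only to the extent that alcohol magnifies it. Section 14 relies on matching stimulus arousal across sessions for 1c.
- 1a, 2a and 2b average over partner type, so this is not a DV-DNV issue for them.

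**4. Illustration for 1b.** The plan gives no alpha, effect size, SD or power calculation, so there is no stated figure to reproduce. From the documents: n = 112 per group. Assumed: two-sided 0.05, independent groups, normal approximation, no true difference, and δ in SDs of each participant's evocative-minus-neutral contrast.

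SE = √(2/112) = 0.134

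P(reject) = Φ(δ/SE − 1.96) + Φ(−δ/SE − 1.96)

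| δ (assumed) | First term | Both terms |
|---|---|---|
| 0 | 0.0250 | 5.0% |
| 0.1 | 0.1128 | 11.6% |
| 0.2 | 0.3216 | 32.2% |
| 0.3 | 0.6122 | 61.2% |

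**The case against.** The strongest reply has four parts.

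*The plan does not say the selector is unmasked.* This is correct. A reader might infer that the PI knows the group and chooses accordingly, but the documents do not support that. Consent may be taken by other staff. The soothing interview depends on a partner's reported mood and can arise in either group. Adverse-event follow-up depends on an event that Section 17 calls rare. Contact arising in the later sessions comes too late to affect clips already cut. No frequency of contact is given. What stands is that masking is not described and that routes to unmasking exist.

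*The hierarchy narrows the choice.* It does, and the relevant pool is about 96 behaviours rather than 192. Choice within a category, cut points and neutral clips are still open.

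*Natural intensity differences would confound 1b even with perfect masking.* This is true, and the plan concedes such differences. It limits what the fix can achieve. It does not justify adding a second, avoidable source that could not be told apart from the first.

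*The size of the shift is invented.* The arithmetic shows what a small shift would do, not that one exists.

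**Conclusion.** The point holds as a gap in procedure. Section 12 has the PI choose the clips, no masking to DV/DNV status is described, and neither safeguard governs the choice of moment, the cut or the neutral clips. The Section 11 assurance is therefore not secured. A reader might go further and conclude that the assurance is false or that the groups' clips do differ through selection. The documents show neither: missing masking is a risk, not evidence of a difference.

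Exposure is mainly in 1b and 2c and smaller in 1c and 2d. It is not a DV-DNV issue for 1a, 2a and 2b. The rise in the 1b false-positive rate to about 12% to 32% is illustrative. It rests on an assumed shift of 0.1 to 0.2 SD and an assumed two-sided 0.05, neither of which comes from the documents. The change is worth making because it is cheap and removes an avoidable source of bias from the DV-DNV contrasts.

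**What to change.** Reconcile Sections 11 and 12 on who selects the clips, and state the following:

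1. The existing trained SPAFF coders select the clips. They work from numeric couple codes, without DV/DNV status or questionnaire data, and have not run that couple's session. The PI does not choose.
2. Across categories, follow the hierarchy. Within a category, draw at random among eligible coded moments. Draw the 25 neutral clips at random from eligible neutral moments.
3. Use fixed cut points around each coded moment.
4. Report the SPAFF category mix of the selected clips by group.

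A random draw is preferable to taking the earliest moments. Section 4 says that arousal in DV couples builds as a conflict goes on, so an earliest-first rule could favour weaker clips, perhaps unequally by group.

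The cost is a procedural paragraph and some reassignment. It needs no new staff, provided that enough current coders were not involved in the couple's session; the plan does not say how the coding team is made up. There are three drawbacks. Speech on the video may sometimes reveal the group. Random draws give slightly less control over clip intensity. Natural DV-DNV intensity differences remain, so 1b should still be interpreted with that limit stated.
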